7.1.1. Temporary Discontinuation (Withholding) of Study Intervention

Infection-related criteria for temporary withholding

Temporary withholding of study intervention is required if the participant meets any of the following infection-related criteria during the study:

 A participant diagnosed with LTBI during the study is to be permanently discontinued from study intervention unless the participant is a candidate for LTBI treatment, and is treated for LTBI as follows:

- Study intervention is temporarily held for at least the first 4 weeks of LTBI treatment.
- After receiving at least 4 weeks of appropriate LTBI therapy (as per WHO or US Centers for Disease Control guidelines), if there is no evidence of hepatotoxicity (ALT/AST must remain ≤2 times ULN) or other treatment intolerance, study intervention may be resumed.
- The participant must complete appropriate LTBI therapy to remain eligible to receive study intervention.
- HBV DNA results that are reported as positive, or as detecting HBV DNA, but HBV DNA is below the level of quantification. The sponsor's designated medical monitor should be contacted regarding study status of the participant. HBV DNA testing is to be repeated as soon as is feasible. If HBV DNA is confirmed as positive, the participant must be permanently discontinued from study intervention (Section 7.1).

Other criteria for temporary withholding

In some circumstances, it may be necessary to temporarily interrupt treatment as a result of AEs or abnormal laboratory values that may have an unclear relationship to investigational intervention. Except in cases of emergency, it is recommended that the investigator consult with the sponsor-designated medical monitor before temporarily interrupting therapy.

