6.7. Intervention after the End of the Study

Interventions available after the end of the study, if applicable, are described in the ISAs.

7. Discontinuation of Study Intervention and Participant Discontinuation/Withdrawal

The following sections describe reasons for

- temporary or permanent discontinuation of a participant's dosing (discontinuation of study intervention), and
- discontinuation (withdrawal) of a participant from the study.

For discontinuation of study sites, of ISAs, or of this master protocol as a whole, see Appendix 10.1, Section 10.1.9.

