7.1. Discontinuation of Study Intervention

Continuing in the study after discontinuation of study intervention

A participant who prematurely discontinues dosing with study intervention is strongly encouraged to remain in the study for safety monitoring through the treatment period and posttreatment follow-up as per ISA requirements.

See this master protocol (Section 8) and the relevant ISA (Section 1.3 [SoA] and Section 8) for data to be collected at the time of discontinuation from the study intervention and for activities in the posttreatment follow-up period and for any further evaluations that need to be completed.

Possible reasons for discontinuation of study intervention

The following reasons for early **permanent** discontinuation of study intervention apply to any ISA conducted under this master protocol.

Note: For laboratory values that meet early permanent discontinuation thresholds, the study intervention should be discontinued unless, in the opinion of the investigator, the laboratory abnormality is due to intercurrent illness or another identified factor. After consultation with the sponsor's designated medical monitor, the participant may be able to continue receiving study intervention. Laboratory tests may be repeated within 1 week to confirm whether discontinuation criteria have been met. Furthermore, if study intervention is not discontinued because of intercurrent illness, the investigator must confirm that the laboratory value no longer meets early discontinuation thresholds after the resolution of the intercurrent illness or other identified factor.

Hepatic event or liver test abnormality

The study drug should be interrupted or discontinued if one or more of these conditions occur:

Elevation	Exception
ALT or AST >8 times ULN	54
ALT or AST >5 times ULN for more than 2 weeks	
ALT or AST >3 times ULN and either TBL >2 times ULN or INR >1.5	In participants with Gilbert's syndrome, doubling of direct bilirubin should be used for drug interruption/discontinuation decisions rather than TBL >2 times ULN.

Elevation	Exception
ALT or AST >3 times ULN with the appearance of fatigue, nausea, vomiting, right upper quadrant pain or tenderness, fever, rash, and/or eosinophilia (>5%)	
ALP >3 times ULN, when the source of increased ALP is the liver	

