ALP >2.5 times ULN and TBL >2 times ULN	In participants with Gilbert's syndrome, doubling of direct bilirubin should be used for drug interruption/discontinuation decisions rather than TBL >2 times ULN.
ALP >2.5 times ULN with the appearance of fatigue, nausea, vomiting, right upper quadrant pain or tenderness, fever, rash, and/or eosinophilia (>5%)	
Source: FDA 2009 and other consensus guidelines, with min	or modifications.

Abbreviations: ALP = alkaline phosphatase; ALT = alanine aminotransferase; AST = aspartate aminotransferase; INR = international normalized ratio; TBL = total bilirubin; ULN = upper limit of normal.

Resumption of the study drug can be considered only in consultation with the Lilly-designated medical monitor and only if the liver test results return to baseline and if a self-limited nondrug etiology is identified.

Abnormal hematology lab values:

- o hemoglobin < 7.0 g/dL (< 70.0 g/L)
- \circ total white blood cell count (WBC) <1500 cells/ μ L (<1.50 × 10³/ μ L or <1.50 GI/L)
- o absolute neutrophil count (ANC) <600 cells/ μ L (<0.60 × 10³/ μ L or <0.60 GI/L)
- \circ absolute lymphocyte count (ALC) <250 cells/ μ L (<0.25 × 10³/ μ L or <0.25 GI/L)
- HBV or HCV: The participant tests positive for HBV DNA (see Section 8.2.7) and clinical
 assessment is consistent with HBV reactivation, or tests positive for HCV RNA
 (Section 8.2.8).

Note: The HBV DNA result is to be confirmed if initial positive test result is positive but below the level of quantification (Section 7.1.1). The participant is to be referred to, evaluated, and managed by a specialist physician with expertise in evaluation and management of viral hepatitis prior to discontinuation of any immunomodulatory and/or immunosuppressive therapy, including study intervention. The timing of discontinuation from study intervention relative to the initiation of any antiviral treatment for hepatitis is to be based on the recommendation of the consulting specialist physician, in conjunction with the investigator, and aligned with medical guidelines and standard of care.

Suicidal Ideation and Behavior: The participant answered "yes" to Question 4 or 5 on the
"Suicidal Ideation" portion of the C-SSRS, or answered "yes" to any of the suicide-related
behaviors on the Suicidal Behavior portion of the C-SSRS. The participant may be assessed
by a psychiatrist or other appropriately trained professional to assist the investigator in

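### Protocol 7.1 and 7.1.1 conflict on HBV DNA found on study: a confirmed trace positive is a mandatory permanent stop, while a quantifiable positive without reactivation is not

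*Protocol*

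**What the plan says.** Three sections of the protocol govern HBV DNA detected after enrolment.

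- **7.1 (permanent stop).** The criterion has two parts joined by *and*: a positive HBV DNA test, and a clinical "assessment is consistent with HBV reactivation". A note asks for confirmation only when the first positive is below quantification. It also requires referral to a hepatitis specialist "prior to discontinuation of any immunomodulatory and/or immunosuppressive therapy, including study intervention", with timing relative to antivirals guided by that specialist. The section says its reasons for early permanent "discontinuation of study intervention apply to any ISA conducted under this master protocol".
- **7.1.1 (mandatory hold).** The HBV criterion is limited to "HBV DNA results that are reported as positive, or as detecting HBV DNA, but HBV DNA is below the level of quantification". The medical monitor is contacted and the test is repeated. Then: "If HBV DNA is confirmed as positive, the participant must be permanently discontinued from study intervention", with a cross-reference to 7.1.
- **8.2.7 (monitoring).** If HBV DNA is detected during the study, drug is to be either held or stopped for good, and the reader is sent to 7.1 and 7.1.1 for the details.

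Restart conditions are written for two other problems. After a liver-test interruption, restart may be considered "only if the liver test results return to baseline and if a self-limited nondrug etiology is identified", in consultation with the medical monitor (7.1). After at least 4 weeks of tolerated treatment for latent TB, "study intervention may be resumed" (7.1.1). No such condition is written for HBV.

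**The concern.** The permanent-stop rules in 7.1 and 7.1.1 use different conditions for the same kind of finding, and the stricter one is attached to the lower viral level. A site holding a quantifiable result with no clinical reactivation, or with the assessment still pending, finds that 8.2.7 requires action but that the sections it cites do not say which action. Two sites could treat identical participants differently, one holding and one stopping, and neither would have a written basis for restarting. These rules are set for every ISA, so the inconsistency carries forward to later interventions.

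There is a secondary statistical link. Protocol 9.3.1 counts permanent discontinuation before the end of treatment as nonresponse and does not name a temporary hold. The choice between the two can therefore affect how a participant is scored, unless an ISA says otherwise.

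**Working it through.** No figure in the plan depends on this, so the check sets the rules side by side.

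**Who can reach the case.** Under 8.2.7, entrants who are HBsAg-negative, anti-HBc-positive and HBV DNA-negative are retested at least every 3 months. BT01 treats for 24 weeks: 24 × 7 = 168 days, and 168 / 30.4 = 5.5 months. At least one retest therefore falls within treatment.

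**What each section requires, read literally:**

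| On-study result | 7.1 criterion met? | 7.1.1 HBV criterion met? | Required action |
|---|---|---|---|
| Below quantification, first result, no reactivation | No | Yes | Hold and repeat |
| Below quantification, confirmed, no reactivation | No | Yes | Permanent stop under 7.1.1, although the 7.1 criterion it cites is not met |
| Confirmed trace or quantifiable, with reactivation | Yes | Trace only | Permanent stop |
| Quantifiable, no reactivation or not yet assessed | No (second part missing) | No (not below quantification) | 8.2.7 only: hold or stop, not stated which |

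The second row is the conflict between the two sections. The fourth row is the uncovered case. Comparing them shows the inverted order: the confirmed trace result must be a permanent stop, and the quantifiable result need not be.

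**Does another reading remove the problem?**

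1. *The cross-reference in 7.1.1 imports the reactivation condition from 7.1.* The second row then becomes a continuing hold, and the word *must* in 7.1.1 no longer means what it says. The fourth row still meets neither criterion.
2. *A quantifiable positive counts as already confirmed, because the 7.1 note asks for confirmation only of trace results.* The 7.1.1 stop would then reach the fourth row. But that sentence sits inside the bullet limited to trace results. On this reading every confirmed positive is a permanent stop, so the reactivation clause in 7.1 would make no difference once a positive is confirmed. The two sections would still disagree.

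**Restart.** None of 7.1, 7.1.1 or 8.2.7 says when dosing may resume after an HBV hold. For the trace hold, resumption after a negative repeat is at most implied through contact with the medical monitor. Appendix 10.2 says only that samples taken with a view to resuming must be assayed centrally.

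**The case against.** The strongest reply is that 8.2.7 already protects the participant. It is mandatory and covers any detected level, so holding is the minimum. That stands. A reader might infer that dosing could continue after a quantifiable positive, or that such a result carries no required hold at all; 8.2.7 rules out both. What it leaves open is hold versus stop.

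Second, the uncovered case may be close to empty. Exclusion criterion 26 treats HBV DNA positivity by PCR as current infection, with no reactivation condition, and a participant who turns positive after a negative screening test may well be judged to have reactivated. If so, 7.1 applies, and so may the opportunistic-infection stop, since Appendix 10.5 lists HBV reactivation. This also stands: nothing shows that the case would be common. It does not reach the participant in whom reactivation is judged absent or is still undecided.

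Third, judgement is available: the specialist referral, the investigator's discretion over laboratory changes, the general interruption text in 7.1.1, and the 7.1 note on laboratory values meeting discontinuation thresholds. The discretionary texts permit action without directing it for this result, the threshold note presupposes a criterion that this case does not meet, and the specialist note sets neither an interim hold nor a restart rule.

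Fourth, a hold on every positive could sit awkwardly with specialist review before discontinuation, since the opening of Section 7 uses that word for temporary as well as permanent interruption. The tension is real, but the present trace hold and 8.2.7 already carry it.

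Finally, a reader might infer that the missing restart rule is peculiar to quantifiable results, or that the gap threatens the efficacy analysis. The first is wrong: the trace hold lacks a restart rule too. The second is not supported: 9.3.1 yields to ISA-specific analyses, and SAP 4.2 leaves intercurrent-event strategies to each ISA's SAP.

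**Conclusion.** The point holds as a minor correction to a patient-safety rule. The stop conditions in 7.1 and 7.1.1 disagree, and read literally the higher viral level has the less strict one. The quantifiable positive without reactivation rests on the either/or in 8.2.7, and no HBV hold has a restart condition.

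The number affected cannot be estimated, because the documents give neither the prevalence of anti-HBc positivity nor a rate of on-study detection. The effect on efficacy results is likely negligible. The conclusion rests on the literal wording of the master protocol; the BT01 ISA was not available and may add its own rule.

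**What to change.** Amend the wording as follows.

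1. In 7.1.1, make the hold apply to any HBV DNA detected on study, quantifiable or not, in line with 8.2.7. Keep the repeat test for below-quantification results, and leave timing relative to antivirals to the specialist, as the 7.1 note provides.
2. In 7.1, make the permanent-stop condition at least as strict for a quantifiable positive as 7.1.1 already is for a confirmed trace positive. With 7.1.1 as it stands, that means not requiring reactivation. The reference in 8.2.7 then leads to rules that cover every result.
3. For any HBV hold, allow restart only after a repeat test in which HBV DNA is not detected and with the medical monitor's agreement.

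The cost is amendment text, with no added participants or scheduled tests; a repeat test is needed only for someone being considered for restart. The downside is possibly a few more holds or discontinuations in the small anti-HBc-positive subgroup, with permanent ones scored as nonresponse under 9.3.1.

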7.2. Participant Discontinuation/Withdrawal from the Study

Data collection and follow-up for participants who discontinue (withdraw) from the study

In rare instances, it may be necessary for a participant to be discontinued early from the study. The participant will be permanently discontinued both from the study intervention and from the study at that time. At the time of discontinuing from the study, if possible, an ETV and any applicable posttreatment follow-up visits should be conducted, as shown in the SoA of the relevant ISA. See this master protocol (Section 8) and the relevant ISA (Section 1.3 [SoA] and Section 8) for data to be collected at the time of discontinuation from the study and for activities to be completed in the posttreatment follow-up period and for any further evaluations that may need to be completed.

Reasons for early discontinuation (withdrawal) from the study

Discontinuation (withdrawal) is expected to be uncommon.

A participant will be discontinued (withdrawn) from the study in the following circumstances:

- at any time at his/her own request, or at the request of his/her designee (for example, legal guardian)
- at the discretion of the investigator for safety, behavioral, compliance, or administrative reasons
- if enrolled in any other clinical study involving an investigational product, or enrolled in any other type of medical research judged not to be scientifically or medically compatible with this study, or
- if the participant, for any reason, requires treatment with a therapeutic agent that is not allowed by the protocol and has been demonstrated to be effective for treatment of the

study indication. In this case, discontinuation from the study occurs prior to introduction of the new agent.

Withdrawal of consent for disclosure

If the participant withdraws consent for disclosure of future information, the sponsor may retain and continue to use any data collected before such a withdrawal of consent. If a participant withdraws from the study, he or she may request destruction of any samples taken and not tested, and the investigator must document this in the site study records.

7.3. Lost to Follow up

A participant will be considered lost to follow-up if he or she repeatedly fails to return for scheduled visits and is unable to be contacted by the study site. Site personnel or designee are expected to make diligent attempts to contact participants who fail to return for a scheduled visit or were otherwise unable to be followed up by the site.

8. Study Assessments and Procedures

Study procedures and their timing are summarized in the SoA of this master IMMA protocol (Section 1.3) and in the SoA of the relevant ISA.

Adherence to the study design requirements, including those specified in the SoAs, is essential and required for study conduct. Since key efficacy data may be collected via an electronic tablet, adherence to the data collection modality specified in the SoA is also essential and is required for study conduct.

Unless otherwise specified in the relevant ISA, efficacy and safety assessments and sample collections should be completed prior to dosing at the dosing visits.

8.1. Efficacy Assessments

Efficacy assessments and endpoints are described in the relevant ISA.

See Appendix 10.8 for descriptions of assessments of disease activity used in the screening period (Visit 1) of this master protocol.

8.2. Safety Assessments

Visits and order of safety assessments

Safety assessments occur at visits specified in this master IMMA protocol SoA (Section 1.3) and in the SoA of the relevant ISA.

If multiple safety assessments are scheduled to occur at the same visit, the preferred order of completion is

- 1) QIDS-SR16, ECG, and then vital signs,
- 2) other safety assessments, including physical examinations, CXR, and nonleading (spontaneous) AE collection, followed by C-SSRS (Section 8.3.1.1), and finally
- 4) sample collection for clinical laboratory, PK, PD, pharmacogenetic, biomarker, and immunogenicity testing.

Data collection and reporting

The AE data collection and reporting requirements are described in Section 8.3 and Appendix 10.3.

For some interventions studied under this master protocol, there may be predefined AESIs. If so, the additional sample or data collections for AESIs will be specified in the ISAs.

Investigator safety monitoring

The principle investigator will monitor the safety data throughout the study. Immediate safety concerns should be discussed with the sponsor immediately upon occurrence or awareness to determine if the participant should continue or discontinue study intervention.

Sponsor safety monitoring

The sponsor will monitor the safety data, including AEs and SAE, discontinuations, vital signs, and clinical laboratory results by means of periodic blinded reviews and by other appropriate

methods. The SAE reports will be reviewed in real time and across studies and will include review of applicable clinical safety and epidemiological publications from the literature. If this safety monitoring activity uncovers an issue that needs to be addressed by unblinding at the individual or group level, members of the IAC can conduct additional analyses of the safety data. The IAC is an advisory group for this study formed to protect the integrity of the study in unblinded safety data reviews. See Appendix 10.1, Section 10.1.5.

Appropriateness of safety assessments

The safety assessments used in this study are routine elements of clinical health assessment and drug development.

Safety assessments described in this master protocol and in ISAs

The following sections describe safety assessments applicable to all ISAs.

See the ISAs for any additional safety assessments which may be applicable to a particular ISA.

8.2.1. Vital Signs

Vital signs will be measured as specified in the SoA of this master protocol (Section 1.3) and in the SoA of the relevant ISA, and as well as whenever clinically indicated. Additional vital signs may be measured during the study visits if warranted, as determined by the investigator.

Blood pressure and pulse rate should be measured after the participant has been sitting for at least 5 minutes.

Unscheduled orthostatic vital signs should be assessed, if possible, during any dizziness or posture-induced symptoms. If the participant feels unable to stand, sitting or supine vital signs will be recorded.

8.2.2. Physical Examinations

Complete physical examinations and symptom-directed physical examinations will be conducted at the visits specified in the SoA of this master protocol (Section 1.3) and in the SoA of the relevant ISA. Symptom-directed physical examinations may also be conducted at other visits, as determined by the investigator, if a participant presents with complaints or as needed per local standard of care.

A complete physical examination should include the following regions and body systems:

- · general appearance
- skin
- head, ears, eyes, nose, throat
- lymph nodes
- cardiovascular
- musculoskeletal
- respiratory
- abdominal
- genitourinary (only as clinically indicated)
- · extremities (tender/swollen joint counts are documented separately), and

neurologic.

The complete physical examination will exclude pelvic, rectal, and breast examinations, unless clinically indicated. The SLE symptom physical assessment is captured in the electronic tablet.

Height and weight

Height without shoes and weight will be measured and recorded as indicated in the SoAs.

8.2.3. Electrocardiograms

For each participant, 12-lead ECGs will be collected as specified in the SoA of this master protocol (Section 1.3) and in the SoA of the relevant ISA. The ECGs should be recorded before collecting any blood samples. Participants must be supine for approximately 5 to 10 minutes before ECG collection and must remain supine but awake during ECG collection.

ECGs may be obtained at additional times, when deemed clinically necessary. Collection of additional ECGs at a particular time point is allowed to ensure high quality records.

ECGs will be interpreted by a qualified physician (the investigator or qualified designee) as soon after the time of ECG collection as possible, and ideally while the participant is still present, to determine whether the participant meets the study entry criteria if applicable, and for immediate participant management if any clinically relevant findings should be identified.

If a clinically significant finding is identified (including, but not limited to, changes from baseline in QT/QTc interval) after enrollment, the investigator or qualified designee, in conjunction with the sponsor's medical monitor, will determine whether the participant can continue to receive study intervention in the study and whether any change in participant management is needed.

The investigator's or qualified designee's review of the ECG printed at the time of collection must be documented. Any new clinically relevant finding will be reported as an AE.

